- *Reduced neurological disability at hospital discharge (Aim 2)*
- *Reduced neuropsychological and functional deficits among survivors at 180 days (Aim 3)*

D.1.2. Overview

Design: Prospective protocol implementation study with an observational comparison group [REOX II (intervention component) versus REOX I (observational component)]

Participants: Adult patients resuscitated from cardiac arrest

Enrollment location: Emergency Departments of 6 urban academic medical centers

Intervention: Implementation of a clinical protocol for rapid FiO₂ optimization after ROSC from cardiac arrest.

Primary outcome: Good neurological outcome (defined as Modified Rankin Scale ≤ 3 ⁴⁵ at hospital discharge).

Secondary outcomes: Neuropsychological tests and ability to return to work among survivors at 180 days.

Mechanistic outcomes: Oxidative stress markers (IsoPs/IsoFs) in plasma 0-6 hours after ROSC.

Estimated sample size and study duration: 280 patients (205 from REOX I and 75 from REOX II).

[figure not shown]
D.2. REOX II Study Protocol

Study setting and population: This study is the second phase in a two-phase study. The initial phase, REOX I, was an observational-only study. As in REOX I, REOX II will identify subjects with return of spontaneous circulation (ROSC) after cardiac arrest in 6 hospitals (Cooper University Hospital, Camden, NJ; Hospital of the University of Pennsylvania and Penn-Presbyterian Medical Center, both in Philadelphia, PA; University of Mississippi Medical Center, Jackson, MS; Methodist Hospital, Indianapolis, IN; and Beth Israel Deaconess Medical Center, Boston, MA). The inclusion criteria are: age > 17 years; cardiac arrest; ROSC achieved; comatose (Glasgow Coma Scale motor score < 6) after ROSC; and clinician intent to treat with target temperature management. The exclusion criteria are: presumed etiology of arrest is trauma, hemorrhage or sepsis; resident of a nursing home or other long-term care facility; known or clinically apparent pregnancy; known lack of commitment to aggressive support by next of kin; and any other condition, that, in the opinion of the investigator, would preclude the subject from being a suitable candidate (e.g. end stage chronic illness with no reasonable expectation of survival to hospital discharge).

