Outcome measures: The primary outcome will be neurological disability at hospital discharge assessed with the Modified Rankin Scale (mRS),^{48,49} a well-validated and widely used outcome measures in stroke clinical trials. The scale runs from 0-6, from perfect health without symptoms to death (**Table 4**). All raters will be trained and certified in mRS assessment⁵⁰ and will use a structured questionnaire and interview, which have been shown to produce very good interobserver reliability.^{51,52} We will measure the Full Outline of UnResponsiveness (FOUR) Score^{53,54} at 72 hours post-ROSC (**Table 5**). The FOUR Score consists of four components with a maximum score of four for each component and allows for assessing intubated patients and brainstem reflexes. We will also perform neuropsychological testing at 180 days after resuscitation for all patients who survived to hospital discharge. We will use an NHLBI-sponsored methodology for performing centralized, telephone-based cognitive testing, which has been previously validated for use in multi-center clinical studies.⁵⁵⁻⁶⁰

Neuropsychological testing will use validated instruments across five cognitive domains: (1) attention, Wechsler Adult Intelligence Scale-IV-digit span; (2) reasoning, Wechsler Adult Intelligence Scale-IV-similarities; (3) immediate and delayed memory, Wechsler Memory Scale-III-logical memory I and II; (4) verbal fluency, Controlled Oral Word Association Test; and (5) executive functioning, Hayling Sentence Completion Test. We will also assess

Table 4: Modified Rankin Scale

Scale	Description
0	No symptoms.
1	No significant disability. Able to carry out all usual activities, despite some symptoms.
2	Slight disability. Able to look after own affairs unassisted, but unable to carry out all previous activities.
3	Moderate disability. Requires some help, but able to walk unassisted.
4	Moderately severe disability. Unable to walk and attend to own bodily needs unassisted.
5	Severe disability. Requires constant nursing care and attention, bedridden, incontinent.

Table 5: Full Outline of UnResponsiveness Score

Component	Scoring
Eye Response	4 = eyelids open or opened, tracking, or blinking to command 3 = eyelids open but not tracking 2 = eyelids closed but open to loud voice 1 = eyelids closed but open to pain 0 = eyelids remain closed with pain

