$$\text{TWA-SaO}_2 = [(SaO_{2a} * \text{Time a}) + (SaO_{2b} * \text{Time b}) + \dots (SaO_{2z} * \text{Time z})] / (\text{Time a} + \text{Time b} + \dots \text{Time z})$$

We will build a multivariable regression model to test the association between TWA-PaO₂ and mRS at hospital discharge, adjusting for covariates previously demonstrated to be associated with poor neurological outcome after cardiac arrest. Covariates to be considered include: (1) pre-arrest comorbidities (Charlson index⁶⁹), (2) prolonged downtime (downtime > 20 minutes) (yes/no), (3) initial arrest rhythm (pulseless electrical activity/asystole vs. ventricular tachycardia/ventricular fibrillation), and (4) arrest location (in-hospital vs. out-of-hospital).⁷⁰⁻⁷⁵ In addition, in order to account for patients with lung injury (i.e. inability to maintain adequate oxygenation) we will add PaO₂/FiO₂ < 100mmHg (yes/no) to the regression model. We will build separate models to test the association between TWA-PaO₂ (adjusting for the five covariates above) and each of the five cognitive domains in our neuropsychological testing. We will then repeat these analyses using TWA-SaO₂ as the exposure variable of interest. This approach will not only allow us to test for an independent association between the exposure and neurological disability and neuropsychological deficits, but will also allow us to pinpoint one or more types of cognitive deficit (e.g. attention, executive function) most closely associated with the exposure. Given outcome measures that are quantitative (i.e. z-score for each cognitive domain) or semi-quantitative (i.e. mRS at hospital discharge), we will treat these outcomes as *continuous* dependent variables for modeling. Using continuous measures of the exposure and outcomes (rather than collapsing the data into categorical variables) will permit detection of subtle effects that could be missed if only categorical analyses were employed.

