Secondary analyses: We will compare proportions of good neurological outcome [defined as a mRS ≤ 3 (based on the preliminary data of our collaborator, [name], University of Pittsburgh)],⁴⁵ between subjects who receive the study intervention (i.e. rapid FiO₂ optimization) vs. those who do not receive the study intervention, using binomial test. Among survivors, we will compare the 180-day neuropsychological measures (composite z-scores for each cognitive domain) between the same two groups using t-test or Mann-Whitney U as appropriate with corrections for multiple comparisons. We will compare the proportions of patients able to return to work between the two groups using binomial test. We will compare plasma IsoPs/IsoFs at each time point between the two groups using t-test or Mann-Whitney U as appropriate with corrections for multiple comparisons.

Sample Size: The sample size calculation in the initial study proposal was based on the primary outcome, mRS at hospital discharge, and we planned to enroll a total of 266 subjects. To ensure adequate power to test the relationships between the above independent variables and cognitive domains, we assumed a medium relationship strength between the six independent variables and each of the five cognitive domains ($R^2 = 0.15$). In order to achieve 80% power and an $\alpha = 0.05$ we would require a minimal of 85 subjects to undergo neuropsychological testing at 180 days. This sample size will be among the largest prospective studies of

neuropsychological outcomes that we are aware of in the literature.^{8,29-32} Assuming a 15% drop out rate for lost to follow up for neuropsychological testing at 180 days we would require 98 subjects to be discharged with a mRS \leq 4. Based on preliminary data from REOX I we expect 35% of patients will be discharged with a mRS \leq 4 and undergo cognitive testing at 180 days. We would therefore require a minimal total sample size of 280 subjects between REOX I and II combined for the multivariable testing. We have enrolled 200 subjects in REOX I to date. We anticipate additional subjects to be enrolled in REOX I and therefore plan for 75 subjects to be enrolled in REOX II to ensure a total sample size of at least 280 subjects.

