Overview of the safety monitoring plan and serious adverse event tracking: In order to help ensure adequate protection of human subjects enrolled in this clinical study, we established an independent three-member **Data Safety Monitoring Board (DSMB)** (see **DSMB Charter**). The Chair of the DSMB will be [name]. [name] is an established investigator and is currently the Director of Clinical Research, Department of Emergency Medicine, Cooper University Hospital, Camden, NJ. The DSMB will be charged with reviewing all serious adverse event reports and will also perform interim analysis of the data after one-third (n=25) and two-thirds (n=50) of the patients have been enrolled in REOX II. Given neither REOX I nor REOX II are blinded, all data reviewed by the DSMB will be unmasked. At both interim analyses the committee will be asked to render a decision as to whether the trial should be continued, modified, or stopped based on the safety profile of the interim data. We have defined the following *a priori* as a reportable serious adverse event (SAE): (1) any events resulting in death or repeat cardiac arrest; (2) sustained hypoxia (defined as $\text{SaO}_2 < 88\%$ for more than three consecutive minutes); (3) heart rate < 50 for greater than one minute; (4) documented cyanosis at any time; or (5) withdrawal of a subject from the trial for any reason. We will define excessive rates of any single SAE *a priori* as a $>15\%$ difference in the prevalence (% of total number in each group) between the two groups [i.e. subjects who receive the study intervention (i.e. rapid FiO_2 optimization) vs. those who do not receive the study intervention] at either interim analysis. A clinician can withdraw a subject from the study for worsening clinical status including worsening respiratory status (based on clinical judgment, arterial blood gas analysis, or increasing FiO_2 requirement). The site PIs at each collaborating institution will be responsible for reporting all predefined SAEs, as well as any other adverse events felt to be related to the study protocol, to the coordinating site, Cooper University Hospital. In addition to reporting all adverse events to the DSMB, all adverse events will be submitted to each institution's IRB for review.

Registration: This study will be registered on clinicaltrials.gov

References

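### Clinicians may withdraw worsening patients from the study itself, and nothing keeps their discharge mRS in the data, so poor REOX II outcomes could be lost

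*Combined protocol and SAP*

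**What the plan says.** **Withdrawal.** The safety monitoring overview in D.2 states: "A clinician can withdraw a subject from the study for worsening clinical status including worsening respiratory status". Clinical judgment, blood gases and a rising FiO2 requirement are given as grounds. The same section lists "withdrawal of a subject from the trial for any reason" among the reportable serious adverse events (SAEs). It calls a rate excessive if the prevalence of any single SAE differs by more than 15% between groups at either interim look (25 and 50 REOX II patients).

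**Outcome.** D.1.2 gives the primary outcome as "Good neurological outcome (defined as Modified Rankin Scale" ≤3 at discharge. The Outcome measures paragraph of D.2 instead says: "The primary outcome will be neurological disability at hospital discharge assessed with the Modified Rankin Scale (mRS"), that is, the whole 0–6 scale.

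**Analysis.** The main model is on the pooled cohort: "We will build a multivariable regression model to test the association between TWA-PaO₂ and mRS at hospital discharge". It has no REOX I versus REOX II term. The group comparison of mRS ≤3 is placed under Secondary analyses and sets subjects who receive the intervention against "those who do not receive the study intervention, using binomial test".

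**What is not there.** No supplied text separates stopping the FiO2 protocol from leaving the study. None says whether mRS is assessed after withdrawal, defines an analysis set, or says how a missing discharge mRS is handled. By contrast, the Informed consent and Therapeutic interventions paragraphs give subjects without surrogate consent within four hours an explicit route to observational follow-up, including discharge mRS and 180-day testing.

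**The concern.** The trigger for withdrawal is deterioration, so any data lost through it would be related to outcome. The protocol's own background supports this for respiratory worsening. In the team's 120-hospital cohort (C.3.1), in-hospital mortality was 57% with hypoxia against 45% with normoxia. In the Australian and New Zealand cohort (A.3) it was 60% against 47%. The Analysis section also adjusts for PaO2/FiO2 below 100 mmHg, so the plan already treats poor oxygenation as something that needs adjustment.

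The loss would probably be lopsided. REOX I patients had clinician-directed FiO2, so a worsening patient there had no study treatment protocol to be taken off. If worsening REOX II patients drop out while equally sick comparators stay in, the REOX II good-outcome rate rises with no treatment effect. Clinician withdrawal is not withdrawal of consent, so it is not in itself a reason to lose the data.

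Defining groups by receipt rather than enrolment adds a smaller ambiguity: the plan does not say where a patient taken off the protocol early is counted.

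**Working it through.** **1. The plan's own loss allowance.** The sample-size paragraph needs 85 subjects tested at 180 days. 85 × 1.15 = 97.75, rounded to 98; 98 / 0.35 = 280. The stated chain reproduces. Its only loss allowance, 15%, is for 180-day testing. Nothing is allowed for a missing discharge mRS, and no stated figure gives the size of this problem.

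**2. Inputs.** From the documents: 75 REOX II and 205 REOX I subjects (D.1.2), and the 15% SAE margin. Assumed: a true good-outcome rate p (mRS ≤3) of 25–35%. The plan expects 35% at mRS ≤4, so on that figure the mRS ≤3 rate cannot exceed 35%; the lower end is a choice. Also assumed: k withdrawn and lost, with good-outcome rate q among them. The worst case is q = 0.

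**3. Shift in the REOX II rate.**

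shift = (75p − kq)/(75 − k) − p = k(p − q)/(75 − k)

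With q = 0 this is p × k/(75 − k):

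| k lost | k/75 | k/(75 − k) | p = 25% | p = 30% | p = 35% |
|---|---|---|---|---|---|
| 4 | 5.3% | 4/71 = 0.0563 | 1.4 points | 1.7 | 2.0 |
| 8 | 10.7% | 8/67 = 0.1194 | 3.0 | 3.6 | 4.2 |
| 11 | 14.7% | 11/64 = 0.1719 | 4.3 | 5.2 | 6.0 |

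If withdrawn subjects do half as well as the rest of the calculation assumes (q = p/2), every shift halves. If they do no worse than average (q = p), it is zero.

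**4. Why stop at 11.** Read the SAE margin as 15 percentage points and assume no comparator withdrawals. Then 11/75 = 14.7% stays under it and 12/75 = 16% does not. The margin is applied only at the interim looks, where the most that stays under it is 3/25 (12%) and 7/50 (14%). Eleven of 75 is therefore a benchmark for the whole group, not a limit that the plan enforces at the end.

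**5. False-positive rate.** Simulation with no true effect, 205 versus 75, the worst-case removal above, and a two-sided 5% pooled z-test standing in for the plan's unspecified binomial test (200,000 runs per scenario, p = 25–35%):

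| k lost | two-sided rejection rate |
|---|---|
| 0 | 5.0–5.2% |
| 4 | 6.1–6.5% |
| 8 | 8.7–10.5% |
| 11 | 11.8–15.6% |

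Almost all of the excess favours REOX II.

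**6. The pooled regression.** Losing the same subjects from the model of mRS on time-weighted PaO2 would bias the slope in a direction that depends on their PaO2 as well as their outcome. The documents do not allow that direction to be derived.

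**The case against.** - **The text does not order any data to be discarded.** A reader might infer that the rule will remove the worst REOX II outcomes. The documents do not support that: they permit withdrawal and are silent on what follows. Consent pages were removed from the supplied text and the DSMB Charter is not included, so retention of data may be covered there. This stands, and the claim is that outcomes could be lost.
- **The group comparison is not the main model.** A reader might infer that the primary analysis is biased in favour of the intervention. The pooled regression has no group term and its bias has no known direction. The clear tilt applies only to the mRS ≤3 comparison, which D.1.2 makes the primary outcome but the Analysis section tests as secondary. This stands.
- **Withdrawals are counted.** They are reportable SAEs with a between-group margin. Fifteen of 75 lost (shift 6.3–8.8 points) would, if spread evenly and absent in comparators, be 5/25 and 10/50. Both are 20% and over the margin, so that scenario is not used. But counting withdrawals does not restore their mRS.
- **The clause is not worded as limited to REOX II.** True. The asymmetry is an inference from the design, hence mainly REOX II.
- **A withdrawn patient did receive the intervention.** This is the natural reading, and nothing says such a patient moves to the comparator. Reclassification is a possible ambiguity only and is not modelled in the figures.
- **The 180-day loss is small in the worst case.** If every withdrawn subject has mRS >3, only those at mRS 4 would be expected to reach cognitive testing. This stands; the main exposure is discharge mRS.

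**Conclusion.** The gap is real. The plan permits withdrawal from the study on a prognosis-related ground, and no supplied text keeps those subjects in follow-up or in the analysis as enrolled. The contrast with the written follow-up route for unconsented subjects makes it more than a matter of style.

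The size is illustrative: about 1.4–2.0, 3.0–4.2 or 4.3–6.0 points on the REOX II good-outcome rate for 4, 8 or 11 lost of 75. This rests on assumed withdrawal counts, an assumed mRS ≤3 rate of 25–35%, no comparator withdrawals, and uniformly poor outcomes among those lost. The last is the worst case, and any good outcome among them shrinks the shift. The finding is a preventable risk to the group comparison of mRS ≤3 and an undirected risk to the pooled regression. It is not a demonstrated bias in either.

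**What to change.** 1. Separate two events in the safety section: stopping the FiO2 protocol, and withdrawal of consent for data. Leave the clinical reasons for stopping as written.
2. State that blood-gas recording, discharge mRS and 180-day testing continue for every enrolled subject unless consent for data is withdrawn. Record the date and reason for each event separately.
3. Define the comparison groups as enrolled, with REOX II being subjects consented and assigned to the protocol, rather than by receipt.
4. Pre-specify how a missing discharge mRS is handled, with a sensitivity analysis counting any missing value as a poor outcome. Keeping all 75 in the denominator removes the shift computed above. If some of those missing in fact did well, this analysis errs against the group with more missing data, so it belongs beside the main result and not in place of it.

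The cost is protocol and SAP wording. The follow-up procedures already exist, and the sample size is unchanged.

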Data collection: We will collect baseline data (e.g. demographics, comorbidities, etc.) and intra-arrest data (e.g. location, initial rhythm, length of downtime, etc.) using the Utstein template for cardiac arrest research⁴⁶ including the recommended variables for post-resuscitation research.⁴⁷ We will capture multiple indicators of post-resuscitation care quality in accordance with the 2010 AHA guidelines.¹² As mandated by the protocol (**Figure 10**) above, our standardized order set for post-resuscitation care will include multiple arterial blood gas (ABG) analyses for partial pressure of arterial oxygen (PaO_2) measurement after ROSC. As part of standard care each institution already obtains ABG analyses at 0- and 6-hours after ROSC. Any additional ABG analyses required to achieve the PaO_2 goal described in **Figure 10** will be considered for research purposes and will be funded by the study. We will record all ABG results over the initial 36 hours after ROSC. We will capture SaO_2 continuously for the initial 36 hours after ROSC. We will also capture every adjustment in FiO_2 from respiratory therapy records and the precise time of the adjustment. We will obtain plasma samples after ROSC at 0- and 6-hours after ROSC and ship the samples to the laboratory of our collaborator [name] (Vanderbilt) for measurement of isoprostanes (IsoPs) and isofurans (IsoFs) by gas chromatography negative ion chemical ionization mass spectrometry (GC/NICI/MS). IsoP and IsoF assays are remarkably stable and therefore are applicable to stored specimens. We can measure IsoPs and IsoFs on clinical plasma samples obtained immediately after ROSC because (after informed consent is secured) we can use samples left over in the clinical laboratory that are routinely discarded.

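### The 15% between-group SAE criterion is not tied to a common way of detecting hypoxia, bradycardia and cyanosis in REOX I and REOX II, so the difference may partly reflect unequal detection

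*Combined protocol and SAP*

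**What the plan says.** The section on the safety monitoring plan and serious adverse event tracking lists the reportable SAEs. They include sustained hypoxia (SaO2 below 88% for more than three consecutive minutes), "heart rate < 50 for greater than one minute", and cyanosis if it is documented. On reporting it says: "The site PIs at each collaborating institution will be responsible for reporting all predefined SAEs". A rate is excessive if there is a more than 15% "difference in the prevalence (% of total number in each group) between the two groups", meaning subjects who receive rapid FiO2 optimization and subjects who do not. The DSMB will "perform interim analysis of the data after one-third (n=25) and two-thirds (n=50) of the patients have been enrolled in REOX II". This is the only numerical safety criterion in the document.

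On the comparison group, Study setting and population states: "The initial phase, REOX I, was an observational-only study". Sample Size adds: "We have enrolled 200 subjects in REOX I to date". The D.1.2 Overview plans 205 from REOX I.

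On detection, Data collection says SaO2 is captured "continuously for the initial 36 hours after ROSC", and Analysis computes a time-weighted average SaO2 over the first 24 hours. Nothing says that the hypoxia SAE is read from that series. No continuous heart-rate capture is described. Under Therapeutic interventions, an on-call investigator talks to the bedside team of each intervention subject and ensures adherence to the protocol. Neither phase is blinded.

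**The concern.** The three events depend on how closely someone looks. A three-minute desaturation or a one-minute bradycardia leaves no lasting trace unless a monitor record is kept and read, or somebody notes it. Cyanosis counts only when it is written down. The intervention group has an investigator in contact with the bedside, plus whatever extra blood gases the oxygen target requires. Most of the comparison group had already been enrolled in an observational study when the plan was written. The reporting duty is in the future tense, and the document describes no look-back.

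If the two percentages are collected differently, their difference mixes harm with detection. A DSMB that sees a hypoxia excess cannot tell which it is. It could react to a false signal, or dismiss a real excess as better reporting. Hypoxia matters most here, because section C.3.3 itself names overshoot in lowering FiO2 as the hazard that the titration protocol must guard against.

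**Working it through.** **Plan figures.** Sample Size has a "plan for 75 subjects to be enrolled in REOX II". One-third is 75/3 = 25 and two-thirds is 2 × 75/3 = 50, so the stated looks reproduce. The criterion has no stated error rate to reproduce. Of the planned comparison group, 200/205 = 97.6% were already enrolled, which leaves 205 − 200 = 5 to come.

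**Inputs.** From the document: a 15-point threshold (its 15% is read as percentage points), looks at 25 and 50, and 200 comparison subjects. Assumed, because the document gives neither: a true rate *p* of 10% to 40%, equal in both groups; full capture in REOX II; and a captured fraction *s* in REOX I of 100%, 80%, 50% or 25%.

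**Expected spurious difference.** Apparent difference = *p* × (capture in REOX II − capture in REOX I) = *p*(1 − *s*).

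- *p* = 20%, *s* = 50%: 0.20 × 0.50 = 10 points.
- *p* = 20%, *s* = 25%: 0.20 × 0.75 = 15 points, which equals the threshold but does not exceed it.
- *p* = 30%, *s* = 50%: 0.30 × 0.50 = 15 points.
- *s* = 80%: 0.10 × 0.20 = 2 points at *p* = 10%, up to 0.40 × 0.20 = 8 points at *p* = 40%.
- *s* = 100%: zero.

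**Chance of a false trigger.** This is P(X₁/n − X₂/200 > 0.15), with X₁ ~ Bin(n, *p*) and X₂ ~ Bin(200, *p·s*), summed exactly over both binomials. It is for one SAE type at one look, in the direction of harm.

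| Look | True rate | *s* = 100% | *s* = 80% | *s* = 50% | *s* = 25% |
|---|---|---|---|---|---|
| n=25 | 10% | 1.6% | 2.8% | 6.3% | 10.1% |
| n=25 | 20% | 4.3% | 9.6% | 25.6% | 47.1% |
| n=25 | 30% | 6.2% | 17.0% | 47.9% | 77.6% |
| n=25 | 40% | 7.3% | 24.1% | 67.5% | 93.1% |
| n=50 | 10% | 0.2% | 0.5% | 1.8% | 4.7% |
| n=50 | 20% | 1.0% | 3.9% | 19.1% | 47.1% |
| n=50 | 30% | 2.0% | 10.0% | 48.0% | 85.9% |
| n=50 | 40% | 2.5% | 17.3% | 73.5% | 98.1% |

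The effect is small when the event is rare or capture is nearly equal. It is large when the event is common and REOX I catches half or fewer.

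**Event by event.**

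- *Hypoxia.* A common objective source is described (continuous SaO2), but the document does not tie the SAE to it.
- *Bradycardia.* No common source is described.
- *Cyanosis.* The event depends on documentation in both groups.
- *Death.* Not affected in the same way, because it is a level of the mRS, which is determined at discharge in the observational component too.

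**The case against.** A reader might infer that only REOX II has SAE reporting and that the REOX I rates are therefore under-counted. The document does not support that. The reporting sentence covers every institution and all predefined SAEs, and it is not limited to REOX II. The criterion is defined over both groups, and the remark on blinding implies that REOX I data reach the DSMB. Subjects who miss the consent window during REOX II have prospective data collection. The DSMB Charter is cited but is not part of the document reviewed, and it may specify ascertainment. So may a separate REOX I protocol, if there is one. No capture rate is given, so no bias has been shown.

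For hypoxia, the continuous SaO2 record weakens the point further, because an objective derivation in both groups may already be possible. The criterion leads to a DSMB judgement and not to an automatic stop, and fuller detection in REOX II would err toward flagging harm.

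Most of this stands and limits the claim to what may happen. It does not remove the point. A future duty to report does not show how events were found in 200 subjects already enrolled, and only about five more are planned. An available SaO2 series does not help if the SAE count is not taken from it. A DSMB can allow for unequal ascertainment only if it knows how each group was ascertained.

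**Conclusion.** The concern holds as a gap with a possible consequence. The plan's one numerical safety criterion compares two percentages without stating that hypoxia, bradycardia and cyanosis are detected by the same source, window and rule in both groups. The difference may therefore partly reflect detection, by an unknown amount. The 10-point shift and the rise from 4.3% to 25.6% at n=25 rest on an assumed true rate of 20% in both groups, half capture in REOX I and full capture in REOX II. With equal capture the shift is nil. Under-counting in REOX I is a risk that the design leaves open; it is not a finding. The gap is clearest for bradycardia and cyanosis. For hypoxia it can probably be closed with data that the plan already calls for. A correction is worth making before the first interim look.

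**What to change.** Add to the safety section:

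> For the between-group criterion at both interim analyses, sustained hypoxia as defined above will be derived in both groups by one algorithm, with one artefact filter, from the SaO2 series captured for TWA-SaO2, over the same hours after ROSC. If the REOX I series was not stored at a resolution that supports the three-minute definition, the DSMB will be told that the hypoxia difference cannot be separated from ascertainment. Bradycardia and cyanosis will be reported to the DSMB for both groups, labelled with their source in each group and flagged as not comparably ascertained unless the source is common.

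Site reporting of individual SAEs to the coordinating site, DSMB and IRBs stays as it is, and no SAE definition changes. Bradycardia and cyanosis should stay in the report for both groups, because dropping the comparison would cost the DSMB its background rate.

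The cost is a small programming task and agreement on an artefact filter for pulse oximetry. Whether new data are needed depends on how the REOX I series was stored. The document does not say, and a time-weighted average alone does not guarantee minute-level resolution. That should be checked first.
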